- Self-management score 18 (of a possible 20) or below on the Diabetes Self-Management Questionnaire (DSMQ)

Exclusion Criteria are:

- Dementia (diagnosis or CDR \geq 1) or prescribed AD medications
- Major medical, psychiatric, or neurological conditions that affect cognitive performance; MMSE <25

- Severe impairment of vision, hearing or fine motor control necessary for computer operation

Eligibility criteria are assessed after potential participants are enrolled by providing signed informed consent at baseline (Visit 1). Following baseline assessment and determination of eligibility, participants are randomized to the CCT intervention, Cognifit, or the active control task. The CCT intervention has games that adapt to the changing performance level of the participant; the active control alternative, has the same games except that they do not adapt to performance, remaining instead at baseline levels. At Visit 2 are introduced to their respective program and are asked perform it 3 days per week (every other day), for 20 minutes, for 24 total sessions. Four months after the intervention, subjects receive a 1-week booster training. Visits 3, 5, and 6 are outcome assessments at the immediate finish of the intervention, six months post-intervention, and 12 months post-intervention, respectively (Figure 1).

[figure not shown]

Figure 1. Timeline of visits from the initial assessments (Month 1; M1) to the final assessments 14 months later.

One of the challenges of internet-based behavior change programs is keeping participants interested and engaged for a sufficient duration, which can be important to ensure a therapeutic benefit. To strengthen participation rates and adherence, staff members call participants once a week, to ask if they are performing the program and if they have any technical difficulties. Nevertheless, we acknowledge that despite these efforts, attrition of subjects occur. Drop out are recorded and Cognifit maintains records, available to this study, of the date and time of each session for each participant in each group.

3. Primary Analysis Objective

The primary outcome measure of this randomized clinical trial (RCT) is the change in DSMQ from baseline (Visit 1) to 6 months after the intervention (Visit 5). The primary analysis is the intent-to-treat (ITT; all enrolled and eligible participants who are randomized) comparison of the two arms of the trial.

4. Analysis Sets/Populations/Subgroups

Intent-to-treat (ITT)

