- Differences between the two arms will be assessed among participants with a Clinical Dementia Rating (CDR) score of zero (i.e., excluding those with uncertain dementia [CDR = 0.5]).
- Differences between the two arms will be assessed among participants with and without at least 12 years of education.
- Differences between the two arms will be assessed by sex.

For each seven secondary outcomes, the primary analysis will like the primary analysis for the DMSQ.

For each primary and secondary outcome, a secondary analysis will include the primary covariates to reduce variation attributable to subject differences.

Analyses by CCT Performance

- Group differences between the two arms will be assessed among participants who complete at least 18 of the 24 CCT training sessions as well as the follow-up visit being examined (i.e. Visit 3, 5, or 6).
- Total time spent training (across all sessions by the participant) are data calculated by Cognifit and available to the investigators. This will be used to explore whether training time modifies group differences.
- CCT performance scores are calculated at each session by Cognifit using assessment measures that remain constant regardless of any changes for the participant. For those with at least 18 of 24 trainings sessions, a linear slope will be calculated to explore whether this modifies group differences.

5. Endpoints and Covariates

Endpoints

The primary endpoint is the change from baseline DSMQ to Visit 5.

Seven secondary endpoints, also change from baseline to Visit 5 (except for medication adherence), are:

- Memory – averaged from neuropsychological tests standardized using baseline scores:

Logical Memory - Immediate Recall

Logical Memory - Delayed Recall

CERAD Word List Memory – Immediate Recall

CERAD Word List Memory – Delayed Recall

CERAD Word List Memory –Recognition

- Executive function/attention – averaged from neuropsychological tests standardized using baseline scores:
 - Cancellation Test - Letter
 - Cancellation Test – Shape
 - Trail Making Test – A
 - Trail Making Test – B
 - Digit Span - Forward
 - Digit Span - Backward
- Prospective memory
 - Rivermead time-based subtest (Appointment)
- Medication adherence – by change in renewals and refills of diabetes medications between one year before Visit 1 and one year after Visit 3
- Hemoglobin A1c (HbA1c)
- Diastolic blood pressure – measured twice while sitting and at rest with a five minute interval

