The third step is to create derived scores for each visit from the new values data of that visit, and the mean and SD of the Visit 1 new values. For every visit, $\text{derived score} = (\text{new value} - \text{Visit 1 new value mean}) / \text{Visit 1 new value SD}$. For Visit 1, the derived score is the z-score, but this is not the case for the other visits, since their derived score is not based on the mean and SD of the new values for that visit. By calculating derived scores this same way at every visit, the participant's change score between a pair of visits is the same as the change for the neuropsychological test, after transformation in the same way as both derived scores for that test. At every visit, derived domain scores for memory and executive functions/attention are sums of the relevant derived scores. By calculating domain scores this same way at every visit, domain change scores between a pair of visits are the weighted sums of the respective change scores for the

neuropsychological tests, with weights based on the transformations of the derived scores.

Medication adherence will be measured by the Continuous, Multiple Interval Measure of Medication Gaps (CMG) method. Using the CPRS diabetes medication refill data, we will identify: 1) refills occurring within one year prior to baseline (Visit 1); and, 2) refills occurring within one year after completion of intervention (Visit 3). To calculate pre-intervention and post-intervention continuous medication gap percentages (CMG), cumulative gaps in medication adherence (the sum of the number of days for which each medication was not available, based on refill amounts and dates) will be divided by the total number of days between the first and last medication fill.

For calculation of linear slope of performance scores, a secondary covariate, we will exclude extreme assessment scores (defined here as above or below 2 standard deviations from the mean – calculated excluding the extreme score itself) since such scores are more likely to be spurious than a true reflection of change.

7. Statistical Methodology

Summary of Study Data

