In contrast to all other outcome measures, which are assessed at each visit and primarily used to compare Visit 1 to Visit 5, medication adherence is measured only twice the year before Visit 1 and the year after Visit 3. The LMM and model are exactly the same except the two times are Visit 1 and a year after Visit 3 for the particular participant.

Measures to Adjust for Multiplicity, Confounders, Heterogeneity, Etc.

As this study may be considered preliminary to a potential subsequent large-scale multi-site study of CCT throughout the VA, each secondary outcome will be tested at the 0.05 level.

Secondary analyses controlling for primary covariates are described in #4, ITT analysis. With regard to secondary covariates, such as ethnicity, health literacy, or computer experience, if any are unbalanced or correlate with an outcome at $p < 0.05$, it will be used as a covariate in a secondary analysis, to reduce within-group variation.

Subject Disposition & CONSORT Diagram

We will report the number of subjects, in each group and in the aggregate, that reached:

- Screen
- Randomization
- Baseline
- At least one follow-up
- Each follow-up

We will also summarize attrition rate and reasons for discontinuation if we have them.

8. Sensitivity Analysis

Not applicable.

9. Interim Analysis

Not applicable.

10. Rationale for Any Deviation from Pre-Specified Analysis Plan

Not applicable

11. QC Plans

All variables are examined for errors.

12. Programming Plan

Data are maintained in Excel files. Statistical analysis will proceed using SAS 9.4, Stata v13.1 and SPSS.

13. Appendices

Not applicable.

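### The post-period for medication adherence is dated only from an attended Visit 3, so randomised participants without that visit have no defined refill outcome

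*SAP*

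**What the plan says.** Section 6 of the SAP takes medication adherence from pharmacy records ("Using the CPRS diabetes medication refill data, we will identify") and summarises it as a continuous medication gap percentage (CMG) before and after the intervention. The post-period is tied to Visit 3 in three places:

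- Section 5, endpoint list: the endpoint is defined "by change in renewals and refills of diabetes medications between one year before Visit 1 and one year after Visit 3".
- Section 6, data convention: the post-period consists of "refills occurring within one year after completion of intervention (Visit 3".
- Section 7, analysis for medication adherence: the mixed model is the one used for the other outcomes, "except the two times are Visit 1 and a year after Visit 3 for the particular participant".

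Section 7 also states that "medication adherence is measured only twice the year before Visit 1 and the year after Visit 3", so each person contributes at most one value before and one after.

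Section 2 describes Visit 3 as an outcome assessment at the end of the intervention, and says of dropout that "we acknowledge that despite these efforts, attrition of subjects occur". Section 3 defines intention-to-treat as all eligible randomised participants, and section 4 says the secondary outcomes are analysed like the primary. Section 6 handles missing data by full-information maximum likelihood, section 7 claims validity under missing at random, and section 8 plans no sensitivity analysis.

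**The concern.** Dropout inevitably removes questionnaire, laboratory and cognitive outcomes, because someone has to attend to provide them. It need not remove a refill outcome. By dating the post-period from an attended visit and giving no alternative, the plan makes this outcome depend on attendance as well.

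The gap may be informative. Section 1 argues that even minor cognitive impairment affects disease self-management, so failing to reach Visit 3 and failing to refill could share a cause. With two measurements per person, the model can condition only on arm and the pre-period CMG, plus any covariates that are added. At stake is whether the randomised comparison for this endpoint uses records that may exist, or an untested assumption in their place. There is also a practical risk: an analyst who notices the gap must choose a substitute date unprompted, possibly after seeing the data.

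**Working it through.** The SAP gives no sample size, standard deviation, attrition rate or power, so there is no figure of its own to reproduce. The check has two parts.

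**Tracing the definition.** Take a randomised participant with no Visit 3.

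1. The pre-period CMG is defined, because it needs only the Visit 1 date.
2. The post-period CMG is not defined, because its window has no start date (sections 5 and 6).
3. The second model time is not defined, because it is one year after a visit that did not occur (section 7).
4. No section supplies a fallback. Section 5 (Calculating time) mentions recorded visit dates, target intervals and logged training dates, any of which could help, but none is assigned to this purpose.

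The participant stays in the mixed model through the pre-period value alone. Someone who stops training early but attends Visit 3 has a date and a post-period value. Someone who misses only later visits is also unaffected.

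**Cost in precision (illustration).** Assume two occasions with equal variance and correlation ρ, and a fraction d in each arm with the pre-period value only. The maximum likelihood estimate of change then has variance, relative to complete data, of

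R = [(1 + ρ)/(1 − d) + (1 − ρ)] / 2,

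and the confidence interval widens by the factor √R. For d = 0.20 and ρ = 0.5: R = (1.5/0.8 + 0.5)/2 = 1.188 and √R = 1.090. A direct generalised least squares calculation gave the same ratios. If complete data would give 80% power, the power becomes Φ((1.960 + 0.842)/√R − 1.960).

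| Missing Visit 3 (assumed) | R, for ρ from 0.3 to 0.7 | CI widening | Power, if 80% when complete |
|---|---|---|---|
| 10% | 1.072–1.094 | 3.5–4.6% | 76–77% |
| 20% | 1.163–1.212 | 7.8–10.1% | 72–74% |
| 30% | 1.279–1.364 | 13.1–16.8% | 67–70% |

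**Conditions for bias.** Let f be the fraction lost in an arm. Let δ be the amount by which the lost participants' true post-period gap exceeds what their arm and pre-period value predict. The error in the arm comparison is then, in size, f_B·δ_B − f_A·δ_A. It is zero if δ is zero in both arms (missing at random), and also if both f and δ are equal across arms. It is non-zero, apart from chance cancellation, if δ is non-zero and f differs by arm, or if δ itself differs by arm. For scale only: losses of 10% and 20% with a common δ of 10 to 20 percentage points give 0.10 × 10 to 0.10 × 20, that is 1 to 2 points. Every input to that line is assumed.

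**The case against.** The strongest defence is that the year after the intervention is a coherent target, in line with Visits 5 and 6, which section 2 also dates from the intervention. The plan does not say that anyone is excluded, and likelihood estimation is a recognised way to handle the missing value. This is one of seven secondary endpoints in a study that section 7 calls possibly preliminary, and the primary endpoint is untouched. Re-dating the window for everyone also changes the endpoint slightly. Much of this stands. It limits the importance of the point and supports the smaller repair as an acceptable one. It does not supply the missing date, and a likelihood method does not justify leaving data missing when they may be obtainable.

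A reader might infer more than the documents support:

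- **That everyone who stops training is lost.** Section 4 treats completing sessions and attending the follow-up visit as separate conditions, and the anchor is the visit.
- **That the analysis becomes complete-case.** Participants with only a pre-period value still inform their arm's baseline mean. The complete-case widening 1/√(1 − d), which is about 5%, 12% and 20% for 10%, 20% and 30% loss, overstates the cost.
- **That training is self-paced, so the window starts systematically later for slow trainers.** Section 2 asks for a fixed schedule of three sessions a week, and section 5 attributes variation in visit dates to scheduling.
- **That the refill outcome would otherwise be nearly complete.** The CMG denominator runs from first to last fill, so a participant with too few fills has no value under any anchor. Access to records after dropout depends on consent terms not given here.

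**Conclusion.** The point holds in a limited form. The three definitions agree with one another, and together they leave the post-period CMG and its model time undefined for any randomised participant without a Visit 3. The loss follows from the definitions and the lack of a fallback; it is not a stated exclusion.

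The size is unknown because the SAP gives no attrition rate. If 10%, 20% or 30% miss Visit 3 and the pre/post correlation is 0.3 to 0.7, the confidence interval for the change widens by about 4–5%, 8–10% or 13–17% under the planned analysis. These figures assume equal loss in the arms, equal variance at the two occasions and common measurement times.

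Bias should not be claimed as a finding. It requires loss that depends on unobserved post-period adherence and differs by arm, or an effect of loss that differs by arm, and the SAP provides no evidence on either. What can be said is that the comparison relies on an assumption where observation may be possible, and that no sensitivity analysis would reveal a failure of it. The amendment is worth making, for a secondary endpoint only.

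**What to change.** Amend sections 5, 6 and 7 together so that one rule sets the start of the post-period. Two versions would work:

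- **Preferred:** a date that every randomised participant has and that does not depend on attendance, for example randomisation plus the planned training period of 24 sessions / 3 per week = 8 weeks.
- **Minimum:** keep Visit 3 where it was attended, and use its scheduled date where it was not.

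In either case, run the window for one year, set the second model time to the same start date plus one year, and extract refills for all randomised participants except those who withdrew consent to record access. Keep the Visit 3-anchored analysis as supportive. Fix the rule before refill data are looked at by arm.

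The cost is a few sentences of SAP text and a refill extract that includes dropouts, with no participant contact. Under the preferred version, the window may include some training weeks for those who finish late. Under both, participants with too few fills to compute a CMG will still be missing, and their number should be reported by arm.

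### The medication-gap score sums gap days over every diabetes drug but divides by one span of days, so it rises with the number of drugs and moves when that number changes

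*SAP*

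**What the plan says.** SAP section 5 lists medication adherence among seven secondary endpoints, measured "by change in renewals and refills of diabetes medications between one year before Visit 1 and one year after Visit 3". Section 6 names the Continuous, Multiple Interval Measure of Medication Gaps (CMG) and calculates one percentage for the year before Visit 1 and one for the year after Visit 3. The numerator is "the sum of the number of days for which each medication was not available, based on refill amounts and dates". It "will be divided by the total number of days between the first and last medication fill".

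Section 7 then analyses the two scores per participant: "The LMM and model are exactly the same except the two times are Visit 1 and a year after Visit 3". Each secondary outcome is tested two-sided at 0.05.

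The SAP has no rule for a drug that is added, stopped or switched. The number of diabetes drugs is not among the primary or secondary covariates in section 5. The score is not limited to drugs present in both windows, and section 8 (Sensitivity Analysis) is marked not applicable.

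**The concern.** The numerator counts drug-days and the denominator counts calendar days. A ratio of the two is not a percentage of anything once a participant takes more than one drug. The endpoint is a change between two one-year windows, separated by a training period of about 24 sessions / 3 per week = 8 weeks, so the regimen has more than two years in which to change. If the number of drugs changes, the score changes even when the participant refills exactly as before. If the number does not change, a given improvement per drug still counts more for someone on three drugs than for someone on one. At stake is whether a difference on this endpoint can be read as a difference in adherence.

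**Working it through.** The SAP gives no sample size, power figure or numeric CMG value, so there is no stated figure to reproduce. The check applies the written formula.

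**Inputs.** The formula is from SAP section 6. The 360-day span, the numbers of drugs and the gap fractions are assumptions, shown over a range.

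**Formula as written.** Score = (sum over drugs of gap days) / (days from first to last fill). With k drugs present over the whole span S, each with gap fraction g, the score is k × g × S / S = k × g.

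**1. Level.**

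| Gap per drug | 1 drug | 2 drugs | 3 drugs | 4 drugs |
|---|---|---|---|---|
| 5% | 5% | 10% | 15% | 20% |
| 10% | 10% | 20% | 30% | 40% |
| 20% | 20% | 40% | 60% | 80% |
| 30% | 30% | 60% | 90% | 120% |

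For example, 10% on two drugs is (36 + 36) / 360 = 20%. The last cell cannot be a percentage of days.

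**2. Change when a drug is added.** One drug before, gap 10%, score 10%. In the second window another drug, also with a 10% gap, covers a fraction f of the span. Score = (36 + 0.10 × f × 360) / 360.
- f = 25%: 45 / 360 = 12.5%
- f = 50%: 54 / 360 = 15%
- f = 75%: 63 / 360 = 17.5%
- f = 100%: 72 / 360 = 20%

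The apparent worsening is 2.5 to 10 points with no change in refill behaviour.

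**3. Change when a drug is stopped.** Two drugs at 10% give 20% before. If one stops at day 180 and its gaps are counted only up to then, the score is (36 + 18) / 360 = 15%. This is an apparent improvement of 5 points.

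**4. Change on any regimen.** With k1 drugs and gap g1 before, and k2 drugs and gap g2 after (all full-window), the change is k2 × g2 − k1 × g1 = k1 × (g2 − g1) + (k2 − k1) × g2.
- The first term multiplies true change by drug count. A fall from 10% to 5% per drug counts as 5 points on one drug and 3 × 5 = 15 points on three.
- The second term is the regimen effect. A participant whose gap falls from 10% to 5% while going from one drug to two scores 2 × 5% − 1 × 10% = 0, so the improvement disappears.

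The random intercept in the section 7 model absorbs stable differences in level between participants. It does not undo either term.

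**5. With a drug-day denominator.** Replace S by the sum of each drug's own days. Level: k × g × S / (k × S) = g, for any k. Added drug at f = 50%: 54 / (360 + 180) = 10%. Stopped drug: 54 / (360 + 180) = 10%. The score stays at the per-drug gap throughout.

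**The case against.** **The denominator may mean a total over drugs.** The SAP names an established method and summarises it in one sentence; the word *total* could refer to all the drugs summed in the numerator. If it meant the sum of each drug's own span, the scaling would vanish. The reading is possible, but the text does not state it, and only the numerator carries a per-drug qualifier. What stands is that programmers could code different endpoints from this sentence, so it needs rewriting either way.

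**With no gaps, nothing scales.** Correct. If gaps are counted within each drug's own span, a participant who refills perfectly scores 0% on any number of drugs. The distortion multiplies gaps that exist and does not create them. The 10-point shift also needs the second drug to cover the whole window.

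**A stronger reading: days when a drug was not prescribed count as gaps.** A reader might infer this because the SAP does not exclude them. A perfectly refilled switch at day 180 would then score (180 + 180) / 360 = 100%, against 0% if gaps are counted within each drug's span. The documents do not support taking this as the plan's rule. The sentence describes gaps in adherence derived from refill amounts and dates, and days before a drug's start or after its prescribed stop are not naturally such gaps. It is an unclosed ambiguity, and the 100% is only its upper end.

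**A stronger reading: the comparison of arms is biased.** HbA1c is itself an outcome, so the intervention might affect prescribing, and an arm with more added drugs could then look less adherent. The SAP gives no drug counts, no rate of regimen change and no difference by arm. Under randomisation, changes unrelated to arm mainly add noise. Bias is conditional and cannot be sized.

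**Limited weight.** This is one of seven secondary endpoints in a study the SAP describes as possibly preliminary; the primary DSMQ analysis is untouched. That limits the importance of the point but does not correct the formula.

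**Conclusion.** The point holds in a limited form. On its natural reading, the section 6 formula gives k × g rather than g, can exceed 100%, moves by 2.5 to 10 points when a second drug with an unchanged 10% gap is added for 25% to 100% of the window, and weights change by drug count on a stable regimen. These sizes rest on assumed gap fractions, drug counts and a 360-day span, and they require non-zero gaps. Nothing elsewhere in the SAP repairs the score. The expected effect is noise and mis-scaling of one secondary endpoint. The SAP does not show bias between arms, nor that unprescribed days are meant to be scored as gaps. The formula should be corrected before this endpoint is analysed.

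**What to change.** Rewrite the section 6 sentence as follows in substance:

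- The score for a window is summed gap days divided by summed drug-days. Each drug's gaps and days are counted only within that drug's own supplied or prescribed period in the window, taken from its fills, or from order start and stop dates if these are available. The score then stays within 0 to 100%.
- Days before a drug's start, or after its prescribed stop or switch, are not gaps.
- Specify this pooled form alone. A simple average across drugs is a different score: drug A at 36/360 (10%) and drug B at 30/60 (50%) average 30%, but pool to 66/420 = 15.7%.
- Report the number of diabetes drugs per window by arm, so that a reader can see whether regimens changed differently.

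The cost is SAP wording and a little extra programming on refill data already being extracted. The SAP does not say that order dates can be obtained. If they cannot, the fills alone will not distinguish a prescribed stop from a participant who ceased refilling, and the report should say so.

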- Systolic blood pressure – measured twice while sitting and at rest with a five minute interval

Primary covariates

- age
- sex
- years of education
- baseline MMSE

Secondary covariates

- site – Bronx, NY VAMC versus Ann Arbor, MI VAMC
- ethnicity – Non-Hispanic European Ancestry vs. Other
- Cognitive Self-Report Questionnaire
- Geriatric Depression Scale
- Short – Test of Functional Health Literacy in Adults
- Total Training Sessions

Calculating time

Dates of Visits 1 through 6 are recorded and individual CCT training dates are maintained by the Cognifit and available for use. As indicated in Figure 1 (above), pre-specified intervals are targeted for each visit, but actual visits vary due to scheduling

contingencies with participants and staff. Thus, intervals between assessments are determined from days since Visit 1 (baseline assessment).

6. Handling of Missing Values and Other Data Conventions

Missing data will be accounted for using iterative full information maximum likelihood estimation of the relevant model parameters.

A separate three-step procedure will be used for the sixteen neuropsychological test scores at each visit. The first two steps substitute values for missing data and the third step creates derived scores for use in analyses.

The first step is limiting the participants for whom their neuropsychological data at that visit will be analyzed. Although most participants have data on all the variables, others have some missing data. A participant's data for a visit will be analyzed only if there are at most two missing variables of the 16. A participant must have data analyzed at Visit 1, but may have data analyzed after missing other visits.

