Descriptive statistics for all relevant variables will be calculated and examined at baseline and subsequent visits. The memory and executive functions/attention scores will be the derived domain scores after taking account of missing data. Substantially non-normal distributions will be transformed to reduce the influence of extreme values. All continuous variables will be summarized using the following descriptive statistics: *n* (non-missing sample size), mean, standard deviation, median, quartiles, maximum and minimum. The frequency and percentages (based on the non-missing sample size) of observed levels will be reported for all categorical measures. All summary tables will be structured by group.

Statistical Procedures

The analytic procedure to address the efficacy of CCT will use linear mixed models (LMM) procedures to evaluate change from baseline (Visit 1) to six months post-treatment (Visit 5). Models will include time (coefficient estimate β_1), intervention group (coefficient estimate β_2), and the intervention group by time interaction (coefficient estimate β_3) which indicates whether the change in outcome over time differs between the intervention groups, all as fixed factors, and subjects as a random factor.

The model for the primary outcome (DSMQ) or any of the seven secondary outcome variables (*Y*) for subject *i* and visit *j* at time t_{ij} is:

$$Y(t_{ij}) = b_0 + b_1 t_{ij} + b_2 \text{Group}_i + b_3 t_{ij}\text{Group}_i + u_i + e_{ij}$$

where b_s estimate the fixed effects of group and time, *u* is the subject random effect, and *e* is the residual error. If the result of randomization is that there is a significant ($P < 0.05$) discrepancy between the two arms of the RCT on any of the primary covariates,

that covariate will be included in the model. Since this estimate will be valid for the ITT population under the MAR assumption, it will not be biased in favor of groups with greater dropout.

Although hypothesized demonstration of benefit of CCT beyond that of the active control is directional, tests of significance will be a two-sided at the 0.05 level, to test for the possibility that CCT is substantially inferior to the active control.

Similar procedures will be employed to compare the treatment arms on change from baseline to other visits for the all outcomes.

Analysis for medication adherence

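### The primary test is one linear slope with no stated visit list; a categorical-visit model would match the Visit 5 endpoint and use Visit 3 data against dropout

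*SAP*

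**What the plan says.** Section 5 (Endpoints): "The primary endpoint is the change from baseline DSMQ to Visit 5".

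Section 7 (Statistical Procedures) fits a linear mixed model with a random subject intercept, one time term, group, and one product of the two. The parameter of interest is "the intervention group by time interaction (coefficient estimate β_3) which indicates whether the change in outcome over time differs between the intervention groups". Time enters as a single continuous variable, and section 5 (Calculating time) states that "intervals between assessments are determined from days since Visit 1 (baseline assessment". There is no visit factor, and no sentence lists the visits that enter the fit.

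Three statements bear on which visits are meant:
- Section 7, on the remaining visits: "Similar procedures will be employed to compare the treatment arms on change from baseline to other visits for the all outcomes".
- Section 7 (Analysis for medication adherence), on all outcomes other than adherence: "which are assessed at each visit and primarily used to compare Visit 1 to Visit 5".
- The same paragraph, on the adherence model: "The LMM and model are exactly the same except the two times are Visit 1 and a year after Visit 3".

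On dropout, section 7 says the estimate is "valid for the ITT population under the MAR assumption, it will not be biased in favor of groups with greater dropout". Section 2 expects attrition and places outcome assessments at Visits 3, 5 and 6. Section 6 allows, for the neuropsychological tests, that a participant "may have data analyzed after missing other visits". Section 8 (Sensitivity Analysis) is marked as not applicable.

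**The concern.** The endpoint is a change between two named visits, while the tested parameter is a slope. Whether the two agree depends on which visits are in the model, and the SAP leaves that to inference. Each reading has a weakness.

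- **Visits 1 and 5 only (more likely).** The slope, scaled to the interval, is close to the Visit 5 effect. But a participant assessed at Visit 3 and then lost contributes only a baseline value. MAR can then condition on baseline score and arm (and any imbalanced covariate that is added), not on the Visit 3 score. If participants who do poorly or well at Visit 3 are the ones who leave, and this differs between arms, the group contrast is biased even though the data that would correct it have been collected.
- **Visit 3, or Visits 3 and 6, also entered (less likely).** Visit 3 then informs the fit, but a straight line is forced through unequally spaced visits, and the Visit 5 difference is misstated whenever the effect is not linear in time.

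At stake is a modest distortion of the primary estimate. No planned sensitivity analysis would reveal it.

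**Working it through.** The SAP gives no sample size, SD, correlation or dropout rate, so there is no figure of its own to reproduce. The checks below use its visit schedule plus stated assumptions.

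**Visit times.** 24 sessions at 3 per week = 8 weeks, about 2 months (Visit 3). Adding 6 and 12 months gives Visits 5 and 6 at 8 and 14 months, which agrees with the 14 months in the Figure 1 caption.

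**1. Two-visit fit: slope against endpoint.** Assume an effect at Visit 5 that does not depend on the exact visit date, within-subject correlation r, and visit-date SD s in months. The slope times 8 months recovers the fraction 1 / (1 + [2/(1+r)]·(s/8)²) of the Visit 5 effect. With r = 0.6, 2/(1+r) = 1.25:
- s = 0.5: 1/(1 + 1.25 × 0.0039) = 0.995
- s = 1: 1/(1 + 1.25 × 0.0156) = 0.981
- s = 2: 1/(1 + 1.25 × 0.0625) = 0.928

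For s = 2 the value is 0.923 at r = 0.5 and 0.932 at r = 0.7. On this reading the mismatch is small.

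**2. Two-visit fit: dropout driven by the Visit 3 score.** Assume no true effect, unit SDs, a common correlation r between visits, and logit(dropout before Visit 5) = a − k·Y3, with a set to give the stated rate. Let mA and mB be the mean Visit 3 scores among those seen at Visit 5 in each arm. Let β be the pooled slope of Visit 5 on Visit 1 among them. Then

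bias = r · (mA − mB) · (1 − β).

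Example with r = 0.6, k = 1, dropout 30% vs 15%: mA = 0.2528, mB = 0.1326, β = 0.5829, so 0.6 × 0.1202 × 0.4171 = 0.030 SD.

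| Dropout, r = 0.6 | k = 0.5 | k = 1 |
|---|---|---|
| same mechanism, 20% vs 20% | 0 | 0 |
| same mechanism, 22% vs 18% | 0.005 | 0.008 |
| same mechanism, 30% vs 15% | 0.017 | 0.030 |
| same mechanism, 30% vs 10% | 0.023 | 0.040 |
| score-dependent in one arm only, 20% vs 20% | 0.023 | 0.042 |
| score-dependent in one arm only, 22% vs 18% | 0.026 | 0.046 |

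Over r = 0.5 to 0.7 the nonzero values run from 0.004 to 0.048 SD. If low scorers leave, the bias favours the arm with more (or with score-dependent) dropout. If high scorers leave, it has the same size and the opposite sign. In simulation (40 runs of 40,000 per arm), adding Visit 3 to the model brought the bias to between −0.001 and 0.002 SD in all 16 cases.

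A separate simulation (400,000 participants, r = 0.6, k = 1 or −1, dropout of 25% to 29%) used stronger contrasts. Score-dependent dropout in one arm only gave 0.06 SD, and opposite mechanisms in the two arms gave 0.12 SD. At an assumed 100 per arm the two-sided type I error would be about 0.07 and 0.13 instead of 0.05. The model with categorical visit and Visit 3 included gave 0.001 SD in both.

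**3. More visits with linear time.** Take a group difference d of 0 at Visit 1 and 1 at every later visit. With complete data the fitted difference at Visit 5 is 8·Σ(t − t̄)d / Σ(t − t̄)².
- t = 0, 2, 8: t̄ = 3.33, so 8 × 3.33/34.67 = 0.77
- t = 0, 2, 8, 14: t̄ = 6, so 8 × 6/120 = 0.40

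**The case against.** The strongest reply is that nothing in the SAP is shown to be false. The assurance on dropout is expressly conditional on MAR, and a two-time mixed model is an acceptable analysis of a two-visit endpoint. Using actual days is a stated response to scheduling variation. The dropout rates, correlations and mechanisms above are all assumed, and several scenarios give negligible bias. All of this stands, and it is why the point is minor.

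Three stronger readings are tempting, and the document does not support them.
- **That the SAP omits Visit 3.** This is an inference. The mention of two times occurs only in the adherence paragraph, the model is indexed by visit, and full-information maximum likelihood does not rule out an all-visit fit. Visits 1 and 5 is the better-supported reading, but it is not stated.
- **That the assurance holds only if dropout is unrelated to Visit 3.** That condition is sufficient, not necessary. When rate and mechanism are equal in both arms, the contrast is unbiased even though dropout follows the Visit 3 score (the 20% vs 20% row with the same mechanism).
- **That the primary analysis would recover only 0.77 or 0.40 of the effect.** This applies only to the less likely reading and to an effect that is sustained rather than linear in time.

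The reply does not remove the need to state which visits enter the primary model, or the fact that Visit 3 data already collected can do useful work.

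**Conclusion.** The point holds as a minor one. The primary model tests a linear slope, its visit list is not stated, and the endpoint is a two-visit change. On the likely two-visit reading, the MAR assurance does not reach dropout that depends on the Visit 3 score and differs between arms in rate or mechanism. The resulting bias is about 0.005 to 0.05 SD in the main scenarios, of unknown sign, and zero with equal rate and mechanism. These figures illustrate and do not bound the effect: more extreme assumed mechanisms gave 0.06 and 0.12 SD. The slope-versus-endpoint mismatch on that reading is about 0.5% to 7% for visit-date SDs of 0.5 to 2 months. On the less likely all-visit reading the dropout issue recedes, but the linear form can misstate the Visit 5 effect. The remedy is the same on either reading, and the severity does not rest on the 0.77 and 0.40 figures.

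**What to change.** For the outcomes assessed at each visit, revise section 7 as follows:
- Fit one mixed model with visit as a category (1, 3, 5, 6), group, visit-by-group terms and unstructured within-subject covariance. Name in advance a simpler covariance structure to be used if the model does not converge.
- Name the group contrast in Visit 1-to-Visit 5 change as the primary test, and take the Visit 3 and Visit 6 contrasts from the same model.
- State MAR as conditional on arm and the observed visits.
- Keep medication adherence as a two-period model, with period as a factor.

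Simply writing that Visits 1 and 5 enter, with visit as a two-level factor, would settle the visit list and match the endpoint. It would leave the dropout point untouched, so it is not enough.

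The cost is a wording change, a few more covariance parameters, and some risk of non-convergence, which the named fallback covers. No new data are needed.
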